8.5 Reporting Procedure

8.5.1 AEs and SAEs

All adverse events and serious adverse events that should be reported as defined in section 8.1.1 will be recorded in the patient's CRF.

Every SAE will be documented by the investigator on the SAE pages (see CRF page 4). The initial report shall promptly be followed by detailed, written reports if necessary. The initial and follow-up reports shall identify the trial subjects by unique code numbers assigned to the latter. The principal investigator will inform the sponsor ([name], Division of Emergencies and Critical Care, Oslo University Hospital) within 24h.

The principal investigator keeps detailed records of all SAEs and performs an evaluation with respect to seriousness, causality and expectedness.

8.5.2 SUSARs

SUSARs will be reported to the Competent Authority. The following procedure will be followed:

The sponsor will ensure that all relevant information about suspected serious unexpected adverse reactions that are fatal or life-threatening is recorded and reported as soon as possible to the Competent Authority in any case no later than seven days after knowledge by the sponsor of such a case, and that relevant follow-up information is subsequently communicated within an additional eight days.

All other suspected serious unexpected adverse reactions will be reported in an unblinded manner to the Competent Authority concerned as soon as possible but within a maximum of fifteen days of first knowledge by the sponsor. In order to keep the investigator and other persons generating data to the study blinded, the unblinding and the reporting will be performed by Department of Clinical Research Support.

SUSARs will be reported using the CIOMS form since Oslo University Hospital is not connected to EudraVigilance.

8.5.3 Annual Safety Report

Once a year throughout the clinical trial, the sponsor will provide the Competent Authority with an annual safety report. The format will comply with national requirements and follow guidelines published at www.norcrin.no.

8.5.4 Clinical Study Report

The adverse events and serious adverse events occurring during the study will be discussed in the safety evaluation part of the Clinical Study Report.

8.6 Procedures in Case of Emergency

Medical treatment of serious events will be according to international guidelines described in local procedures in Oslo University Hospital (E-håndbok). The PI and the sponsor will decide how to handle each serious patient event. Emergencies will be treated as usual, by the personnel specially trained in relevant medical emergencies.

9 The investigator recording of data and source verification

9.1 Case Report Forms (CRFs)

Electronic Case Report Forms (eCRF) will be provided for the recording of all data. The software Viedoc™ Version4, approved by local data protection office at OUH, serves as base for the eCRF. Every investigator responsible for entering data into the eCRF will be provided with a unique identity and password, thereby creating an electronic signature of the investigator attesting the accuracy of the data on each eCRF. If any assessments are omitted, the reason for such omissions will be noted on the eCRFs. Corrections, with the reason for the corrections if applicable, can easily be traced by date and signature in the eCRF.

9.2 Source Data

The medical records for each patient should contain information which is important for the patient's safety and continued care and to fulfill the requirement that critical study data should be verifiable. To achieve this, the medical records (MetaVision electronic anesthesia version (MV), or DIPS, or similar of each patient should clearly describe at least:

- That the patient is participating in the study, e.g. by including the enrollment number and the study code (CarbetocinHeart2014)(MV);

- Date when ICF was obtained from the patient and statement that patient received a copy of the signed and dated ICF (DIPS);
- Results of all assessments confirming a patient's eligibility for the study (DIPS);
- Diseases/patient history (past and current; both the disease studied and others, as relevant) (DIPS);
- Treatments given, changes in treatments during the study and the time points for the changes (MV);
- Non-Serious Adverse Events and Serious Adverse Events (if any) including causality assessments (MV);
- Date of, and reason for, discontinuation from study treatment (DIPS);
- Date of, and reason for, withdrawal from study (DIPS);
- Additional information according to local regulations and practice (DIPS).
- Some blood analyses will be analyzed consecutively (Hb and Na) and these data will be entered into the database when made available.

Troponin I analyses will be performed in one batch when all patients are included and the follow up period is over (48h). A biobank consisting of blood samples marked by patient number (not initials or any person identification) will be established. This biobank will consist of aliquots of plasma, stored in a certified biobank freezer (-70 °C), and transported to department of clinical biochemistry, Vestre Viken Trust– Drammen Hospital for final analyses.

- Electronic files, including the data from CRF entered into an electronic database software (Viedoc™ Version4), will be stored at the research server at Oslo University Hospital. This data storage is administered by the Data Inspectorate's local representative who also will handle the application for approval of data storage and ICF.

9.3 Source Data Verification

The investigator will be visited on a regular basis by the Clinical Study Monitor, who will check and collect completed CRFs, discuss the progress of the study and monitor drug usage according to ICH GCP. The monitoring will also include source data verification (SDV).

All data will be entered into a computer database at Oslo University Hospital for further handling.

Sponsor's representatives, Department of Clinical Research Support, and Norwegian Medicines Agency will be allowed access to source data for source data verification in which case a review of those parts of the hospital records relevant to the study may be required.

9.4 Storage of Study Documentation

The patient identification and the code list will be kept by the PI in a locked office. Patient files will be kept for the maximum period of time permitted by each hospital. The study documentation (CRFs, Site File etc) will be retained and stored during the study and for 15 years after study closure. All information concerning the study will be stored in a safe place inaccessible to unauthorized personnel.

10 Statistical considerations

10.1 Determination of Sample Size:

Based on the primary endpoint of interest, Troponin I, group size in order to detect statistically significant differences between the two treatments will be calculated. This is the first clinical study comparing these outcome measures and calculation of statistical power and group size estimations will be calculated from a stage one study/pilot study including 40 patients. Inclusion of patients in the pilot trial was completed in June 2018. In this double blinded randomized controlled pilot trial, elective healthy C-section patients were randomized to oxytocin 2.5 U or carbetocin 100 µg. Plasma level of troponin I was measured at 0h, 4h, 10h and 24h after administration of study drug. The largest difference in plasma troponin I level was found at 10 hours, mean change 0.41 (SD 0.79) in group A versus mean change of 1.78 (SD 4.48) in group B.

Statistical power analysis and group size estimation have been performed by a medical statistician ([name]), based on the results from the pilot trial. We will need to include a minimum of 178 patients in the confirmatory trial. In the part-2 study, troponin I level will be measured at two time points, at baseline and at an interval of 6-10 hours after administration of study drug. To adjust for reduced number of troponin I measurements, missing values and drop outs, 240 patients will be included in the larger confirmatory study, CMT-part 2.

The same protocol that lay the foundation of the pilot trial will serve as protocol for the larger follow up study including 240 patients.

10.2 Randomization and blinding

After inclusion patients will be randomized to one of two arms. Randomization list will be made by a researcher not involved in the data collection using randomization software. The randomization responsible will decide block size and if variable block size will be used. Randomization will be initiated at the first registration of the patient in the electronic CRF, however the result of the randomization with regard to the treatment allocation will be unavailable to all the members of the study team with the exception of the person responsible for preparing the syringes and the person generating the randomization list. These persons will not be the same as the one responsible for analysis of the trial data. A detailed procedure for the person responsible for preparing the syringes is stored in the Investigator Site File at the respective study site.

Department of Clinical Research Support will be responsible for sending SUSARs to the Competent Authority and will also have a randomization list available. Unblinding of one or more patients will be performed by this third party only.

In case of need, emergency unblinding of one single patient with regard to treatment allocation may be performed by the personnel responsible for preparation of study drug or by the principal investigator, as described under 8.6.

Blinding of study drug will be secured by using standard 10-ml syringes marked with information as described under 5.8.

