3.3 Inclusion Criteria

1. Healthy pregnant women age 18 to 50
2. Singleton pregnancy at gestational age 36 weeks or more
3. Able to read and understand Norwegian.
4. Patients will be recruited from the general population at the birth clinic at Oslo University Hospital or the birth clinic of Akershus University Hospital. Signed informed consent form (ICF) and expected cooperation of the patients for the treatment and follow up will be obtained and documented according to ICH GCP, and national/local regulations.

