5.5 Concomitant Medication

In case of uterus atony, patients will be treated with oxytocin 1 U every 2 minute up to maximum 5 U. Any additional treatment of uterus, medical or surgical, will be decided by the attending obstetrician and anesthesiologist according to departmental procedures. Spinal anesthesia will be given according to departmental procedure, hypotension prophylaxis (phenylephrine 0.1 mg/ml) and intravenous volume (normal saline 10 ml/kg starting concomitantly with spinal anesthesia (see 6.2.2 for details). Pain intensity and opioid consumption will be registered for the patients included at Rikshospitalet, OUH, only. For these patients (Rikshospitalet, OUH) pain treatment protocol includes oral paracetamol 1 g and ibuprofen 400 mg 4 times pr day and IV morphine administered according to departmental procedure using a patient controlled analgesia pump (PCA). All interventions, including all administered medication will be registered with doses and timing.

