6.2.2 During Treatment

Vital signs, preoperative pain status, and baseline blood samples will be registered before anesthesia. Spinal anesthesia will be given according to departmental procedure. During surgery, the patient will be supine with a left lateral tilt (operating table tilt, or operating wedge under her right hip). Hypotension (systolic arterial pressure <90 mmHg) is treated with an extra i.v. bolus of phenylephrine if the heart rate is above 60 beats/min or with i.v. ephedrine 5–10 mg if 60 beats/min or below. The level of anesthesia will be tested by cold sensation 5 min after spinal anesthesia as well as by pinching with surgical tweezers before horizontal skin incision (Pfannenstiel). The study drug will be injected slowly, over the course of 60 s, starting when the baby's head and shoulders are delivered. Exteriorization of the uterus is performed routinely according to departmental policy. The patient will be asked if she experienced any of the listed side effects, and to grade the intensity of the side effects as mild, moderate, or severe. The duration of the side effects will also be recorded. Side effects, pain intensity and medications will be registered until 48h. Registration of side effects will be performed at the following intervals, 0–2 minutes, 2–5 minutes and 5–10 minutes after study drug administration. The rest of the observation period side effects will be registered when reported by the patient.

The obstetrician in charge of the Cesarean delivery assess uterine tone 2.5, and 5 min after administration of study drug, using a numeric rating scale that range from 0 to 10, where a score of 0 means "no effect", 10 means "maximal uterus contraction", and 7 indicates "clinically satisfactory contraction". This uterine contraction scale was introduced to the obstetricians earlier in a previously published RCT. Because visual assessment of blood loss during delivery is of limited value, we will calculate estimated blood loss using the formula for calculated estimated blood loss as published by Stafford(5), revised with weight in kg (last measurement prior to operation), height in cm.(1)

Routine assessments of newborn status are registered (Apgar 1 and 5 minutes, umbilical vein and artery acid-base status).

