2.1.2 CMT2 trial

240 patients will be included into the CMT2 trial from the general population of the birth clinics of OUH and Akershus University Hospital (AHUS).

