7.4.2 Repeated-measures continuous outcomes

The primary endpoint and all other continuous endpoints, including baseline and ≥ 1 follow-up measurements, will be analysed with linear regression models, with the follow-up measurement defined as the dependent variable and treatment group and baseline measurement defined as independent variables. Based on the fitted models, we will estimate treatment group differences in changes from baseline with 95% confidence intervals (CIs), together with a p-value for the null hypothesis of no treatment group difference. We expect at least some degree of skewness in the primary and some of the secondary endpoints, and maybe also in the residuals from the linear regression models. The amount of skewness will be assessed with histograms and descriptive statistics, such as mean, median, variance, and the skewness index. In cases where the distribution of the residuals deviates markedly from the normal distribution, or when the endpoints themselves are too skewed to use means as measures of central tendency, we will use median regression models instead of linear regression models, thus analysing between-group differences in median changes from baseline instead of mean changes from baseline. Standard errors and CIs in the median regression models will be obtained via bootstrapping with 100 replications.

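### CMT2 recruits at two hospitals, but the primary regression has no hospital term and the documents do not say whether randomisation is stratified; adding the term is a minor, nearly free improvement

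*Protocol*

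**What the plan says.** **Two hospitals.** SAP 2.1.2 states "240 patients will be included into the CMT2 trial from the general population of the birth clinics of OUH and Akershus University Hospital (AHUS"), and Protocol 3.3 names "the birth clinic at Oslo University Hospital or the birth clinic of Akershus University Hospital". The pilot recruited at OUH only (SAP 2.1.1), so hospital is a new source of variation in CMT2.

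**Care after baseline.** Protocol 5.5 says "Spinal anesthesia will be given according to departmental procedure", and that uterine treatment beyond the first-line atony regimen "will be decided by the attending obstetrician and anesthesiologist according to departmental procedures". Protocol 6.2.2 adds "Exteriorization of the uterus is performed routinely according to departmental policy".

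**Randomisation.** Protocol 10.2 describes a computer-generated list for two arms, then says "The randomization responsible will decide block size and if variable block size will be used". SAP 7.2 delegates the same choice. Neither section mentions strata.

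**Analysis.** The SAP 7.4.2 models, for continuous outcomes with a baseline and a follow-up value, have "treatment group and baseline measurement defined as independent variables". If skewness is marked, median regression replaces linear regression. SAP 7.4.3 and 7.4.4 use Welch, Fisher mid-P and Wilcoxon-Mann-Whitney tests, all without hospital. The analyses listed in SAP 7.4.1 and 7.4.5 include none by hospital.

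**The concern.** Blocks keep the arms equal in number over the whole list. If one list serves both hospitals, they do not keep the arms equal within each hospital, so the hospital mix can differ between arms by chance. If troponin change also differs between hospitals, part of the residual variation is hospital variation that a simple covariate could remove.

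If instead the list is stratified, the balance is built in but the analysis ignores it. The model then counts hospital variation as error, although that variation cannot affect the treatment comparison, and the confidence interval is wider than it needs to be.

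In either case a hospital term is the natural companion to a two-hospital design. What is at stake is a small amount of efficiency, not the validity of the result.

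**Working it through.** **1. Inputs.**
- From SAP 7.1.2: change from baseline 0.41 (SD 0.79) ng/L with carbetocin and 1.78 (SD 4.48) ng/L with oxytocin; target difference 1.37 ng/L; 5% significance level; 80% power; 178 required (89 per arm); 240 enrolled. Two-sided testing is from SAP 4.2 and the 1:1 ratio from SAP 2.1.
- Assumed, because the documents do not give them: the split between hospitals (50/50 to 80/20) and the difference in troponin change between hospitals.

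**2. The plan's own figure.** A Welch t-test with Satterthwaite degrees of freedom and a noncentral t distribution gives power 0.798 at 88 per arm and 0.803 at 89 per arm. The stated 178 is reproduced exactly, and it does not depend on hospital.

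**3. Chance imbalance if the list is not stratified.** With 1:1 allocation the number of women from one hospital in an arm is hypergeometric.

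| Number analysed | Hospital split | 95% range of difference in hospital share between arms | P(10 points or more) |
|---|---|---|---|
| 240 | 50/50 | ±12.7 points | 0.155 |
| 240 | 80/20 | ±10.1 points | 0.075 |
| 178 | 50/50 | ±14.7 points | 0.230 |
| 178 | 80/20 | ±11.8 points | 0.092 |

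A single blocked list shared by two equal hospitals in random order (block size 4, 6 or 8) gives about 0.16 at 240, so blocking alone does not remove the imbalance.

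**4. Translation to the estimate.** The average SD is √((0.79² + 4.48²)/2) = 3.217 ng/L. With 120 per arm the treatment SE is 3.217 × √(2/120) = 0.415 ng/L. With a 50/50 split, the SD of the difference in hospital share is about √(0.25 × 4/240) = 0.0645. For a true hospital difference *g*, the 95% range of the chance shift is ±1.96 × 0.0645 × *g*:
- *g* = 0.5 ng/L: ±0.06 (5% of 1.37)
- *g* = 1 ng/L: ±0.13 (9%)
- *g* = 2 ng/L: ±0.25 (18%)

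This shift has mean zero and is part of the sampling error that the unadjusted SE already counts.

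**5. Precision lost, list unstratified.** With a 50/50 split and a hospital effect of *d* SDs, the residual variance without the term is larger by the factor 1 + *d*²/4, so the SE is larger by √(1 + *d*²/4):
- *d* = 0.2 (0.64 ng/L): √1.01 = 1.005, or 0.5%
- *d* = 0.5 (1.61 ng/L): √1.0625 = 1.031, or 3%

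**6. Type I error.** Simulation under no treatment effect, with 240 women, a 60/40 split, normal residuals with SD 3.217 and 6,000 runs per setting:

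| Hospital effect (ng/L) | Unstratified, no term | Unstratified, with term | Stratified, no term | Stratified, with term |
|---|---|---|---|---|
| 0 | 0.052 | 0.053 | 0.051 | 0.051 |
| 1 | 0.053 | 0.054 | 0.043 | 0.046 |
| 2 | 0.050 | 0.051 | 0.041 | 0.051 |
| 4 | 0.056 | 0.054 | 0.022 | 0.053 |

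The mean estimate was within 0.01 ng/L of zero in every setting. Unstratified, at 2 ng/L, the SD of the estimate was 0.432 without the term and 0.413 with it.

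The conservative entries agree with a direct calculation. Under stratification the model's SE is too large by √(1 + 0.24*g*²/3.217²), which is 1.045 at 2 ng/L and 1.171 at 4 ng/L. The two-sided normal tail beyond 1.96 times these factors is 0.040 and 0.022.

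**The case against.** Much of the case against making more of this stands.

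- **A reader might infer that the list is unstratified.** The documents do not say so. The sentence on blocks concerns block size only, and neither Protocol 10.2 nor SAP 7.2 rules strata in or out.
- **A reader might infer that chance imbalance between hospitals would bias the trial.** It does not. Randomisation makes the imbalance zero on average, the SE covers it, and the simulated type I error without stratification or a hospital term stayed at 0.050 to 0.056.
- **A reader might infer that care differs widely between the hospitals.** No passage says that it differs. The first-line treatment of atony, the hypotension treatment and the uterine tone scale are common to the protocol, and blood loss is calculated by formula. The documents also give no ground for expecting sampling times within the 6-10 h window to differ by hospital.
- **Other parts of the plan already help.** Baseline adjustment accounts for hospital differences in troponin level before treatment, and analysis in one batch at one laboratory limits assay differences. Neither reaches care after baseline.
- **The assumed hospital effects are generous.** An effect of 0.5 SD is 1.61 ng/L, more than the 1.37 ng/L that the trial is powered to detect, and it costs only 3% in SE. The variance formula is for linear regression and does not carry over directly if median regression is used.
- **The change is not free everywhere.** A fixed term cannot be added to the Welch, Fisher mid-P or Wilcoxon-Mann-Whitney tests without replacing them, and a 0.5% to 3% gain does not justify that.

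These points limit the size of the issue and the reach of the fix. They give no reason to leave hospital out of the regressions, where the term costs almost nothing and helps whether or not the list is stratified.

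**Conclusion.** This is a minor, free improvement. The documents establish two hospitals, some care by departmental procedure, no stated stratification factor, and a primary regression with no hospital term. They do not establish an unstratified list, a difference in practice between hospitals, or any threat to validity.

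The size depends on assumptions that the documents cannot settle. Unstratified, with a 50/50 split, the SE is 0.5% larger at a hospital effect of 0.2 SD and 3% larger at 0.5 SD. Stratified, with a 60/40 split, the actual type I error falls to about 0.04 at 2 ng/L and 0.02 at 4 ng/L; the second is an extreme case. If the hospitals do not differ, nothing is gained and nothing material is lost.

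**What to change.** 1. **SAP 7.4.2:** before unblinding, add hospital (OUH or AHUS) as a fixed covariate in the regression models, linear and, if used, median, for troponin I and the other baseline-adjusted continuous outcomes. In CMT2 these include haemoglobin and sodium. The cost is one degree of freedom per model; the required 178 is unchanged. The timing matters because a term added after unblinding could look data-driven.
2. **Protocol 10.2 and SAP 7.2:** state whether the list is stratified by hospital. If enrolment has not started, stratify the blocked list by hospital, which is a setting in the randomisation software. If it has started, leave the list alone and add only the covariate.
3. **SAP 7.4.3 and 7.4.4:** leave the Welch, Fisher mid-P and Wilcoxon-Mann-Whitney tests unchanged.
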